7.2 Sample size considerations

A priori sample size calculation was performed on the basis of an estimated Cohen's *d* effect size of 0.8, which is considered large and acceptable for a teaching intervention.³³ We aim at a two-tailed level of significance of $p < 0.05$ and a power of 0.8. Using the recommended sample size estimation approach for ANCOVA³⁴ with an estimated r^2 of 0.12, derived by a previous, not now published trial ([name] et al, Learning crisis resource management: Practice versus observing, CAS 2013 Abstract 1653689, accessible at <http://www.cas.ca/English/AM-Abstracts-2013>), a number of 46 participants would be needed. In order to account for an estimated attrition rate of 20% we need to recruit 56 participants. G*Power for MAC (version 3.12, Düsseldorf, Germany) was used for sample size calculations.

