7.3 Statistical analysis

As it has been suggested as best practice for stratified randomized controlled trials, ANCOVA will be used to analyze the outcome parameters using the level of training (PGY1-3 vs PGY 4-5 and fellows) and specialities (acute care specialities vs. non-acute care specialities) as covariates.³⁵ Group assignment (unexpected death, alive) will be used as the independent variable. Demographic data will be analyzed using an unpaired Student's *t*-test or chi-square test, where appropriate.

Curved/linear regression analysis will be performed to assess the correlations between each outcome and stress as well as emotions. As it is common practice, results of Likert-like scales will be treated as interval-measures and thereby analyzed by using parametric tests.^{36,37}

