Impact of Unexpected Death in Simulation: Skill Retention, Stress and Emotions

Data Analysis Plan

Primary Outcome: Difference in retention of non-technical crisis resource management (CRM) skills using Ottawa Global Rating Scale (OGRS)

ANCOVA:

- Dependent variable: OGRS score (total score)
- Independent variable: Death vs. survival
- Covariates: Junior vs. senior; Acute vs. non-acute

Secondary Outcome 1: Technical CRM skills (according to checklist)

- Same Videos to be provided for primary outcome will be scored using the “Task-specific checklist” (derived from American Heart Association’s Megacode Checklist) and given a score out of 18

ANCOVA:

- Dependent variable: Task-specific checklist score (total score)
- Independent variable: Death vs. survival
- Covariates: Junior vs. senior; Acute vs. non-acute

Secondary Outcome 2: Stress

Measure 1: Salivary cortisol

Five time points (minutes passed since baseline):

1. Baseline (0 minutes) during the accommodation period at the beginning of the day
2. Before scenario (10 minutes)
3. Immediately after scenario (30 minutes)
4. 30 minutes after start of scenario (45 minutes)
5. After debrief (50 minutes)

ANCOVA:

- Dependent variable: Change in cortisol concentration (versus baseline) at a given time point (for each time point)
- Independent variable: Death vs. survival
- Covariates: Junior vs. senior; Acute vs. non-acute

Regression:

- Linear regression to determine the effects of covariates (Junior vs. senior; Acute vs. non-acute) on change in cortisol concentration over time
 - Separated into “death” and “survival” groups
 - Change in cortisol concentration will be established using the baseline reading of each participant on each day of the study (time point 1).
- Unpaired t-tests will be used to compare change in cortisol levels between the “death” group and the “survival” group at each time point.

Measure 2: State-Trait Anxiety Inventory (STAI)

- Analysis will be carried out in the same way as the cortisol measures with the STAI score taking the place of the change in cortisol concentration

Measure 3: Cognitive appraisal

- Mean cognitive appraisal ratios for each group (“death” and “survival”) at each time point will be calculated and subjected to a one-sample t-test to determine whether they are significantly different from 1.
- Unpaired t-tests will be used to compare the mean ratios of the “death” and “survival” groups at each time point.

Secondary Outcome 3: Valence of emotions

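### For cortisol and STAI the SAP tests each death-versus-survival contrast twice, once without the stratification factors, and does not say which result governs

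*SAP*

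**What the plan says.** Protocol 6.2 stratifies randomisation by level of training and by acute-care specialty, in blocks of 4, partly to gain power. Protocol 7.3 draws the consequence: "ANCOVA will be used to analyze the outcome parameters using the level of training" and specialty as covariates, with group as the independent variable. The only use 7.3 gives to the unpaired t-test is the comparison of demographic data. Protocol 7.1.2 lists salivary cortisol, cognitive appraisal and STAI among the secondary outcomes, so 7.3 covers all three.

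The SAP, under Secondary Outcome 2, Measure 1, first sets out an ANCOVA of change in cortisol from that day's baseline, at each time point, death versus survival, adjusted for both strata. It then adds, printed under the regression heading: "Unpaired t-tests will be used to compare change in cortisol levels between the" same two groups, again at each time point. For STAI (Measure 2) it says: "Analysis will be carried out in the same way as the cortisol measures", with the STAI score as the response. For cognitive appraisal (Measure 3) the between-group comparison is by unpaired t-test only. The t-tests are not labelled descriptive, supportive or sensitivity analyses, and no order of precedence is given.

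**The concern.** The response, the groups and the time points of the two cortisol analyses are the same. They differ only in whether the stratification factors are in the model. Each contrast therefore gets two p-values and two confidence intervals, and the plan does not say which one is the result.

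The two are not equally sound. Stratified blocks balance the strata across arms, so the estimated group difference carries little between-stratum variation. The unadjusted t-test still counts that variation in its standard error. If the strata predict the outcome, its interval is too wide and its power is lower than the data allow. In a trial of this size, a reported absence of difference in stress could come from the weaker test alone.

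**Working it through.** **Inputs.** Protocol 7.2: "We aim at a two-tailed level of significance of $p < 0.05$ and a power of 0.8"; an "effect size of 0.8, which is considered large and acceptable for a teaching intervention"; ANCOVA "with an estimated r^2 of 0.12"; "a number of 46 participants would be needed". Protocol 6.2: 1:1 allocation, two binary stratification factors (four strata), blocks of 4. The r² and d in 7.2 belong to the sample size calculation. Neither is given for cortisol or STAI, so R² is varied over 0.05, 0.12 and 0.30, and d = 0.8 is borrowed.

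**The plan's own figure.** A two-sample t-test with d = 0.8, two-sided 0.05 and power 0.80 needs 26 per arm, 52 in total. Multiplying by (1 − r²): 52 × 0.88 = 45.76, rounded up to 46. The stated number reproduces.

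**Number of duplicated contrasts.** Protocol 6.1.3 has five cortisol samples per session over two sessions: 4 changes from baseline × 2 = 8 contrasts. STAI is taken twice per session: 2 × 2 = 4. That is up to 12 contrasts, each tested twice, so up to 24 p-values.

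**Standard error.** With total SD 1 and 23 per arm, the t-test uses √(2/23) = 0.295. If the strata are balanced, the true standard error is 0.295 × √(1 − R²). The inflation factor is 1/√(1 − R²): 1.026, 1.066 and 1.195 for R² of 0.05, 0.12 and 0.30.

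**Type I error of the t-test.** 2 × P(t₄₄ > 2.015 × inflation). At R² = 0.12 this is 2 × P(t₄₄ > 2.148) = 0.037.

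**Power.** The noncentrality is 0.8/(0.295 × √(1 − R²)), which is 2.89 at R² = 0.12. For the t-test the critical value is 2.015 × inflation on 44 df. For ANCOVA it is the usual t critical value on 42 df.

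A simulation (46 people, four equally likely strata, blocks of 4; 20,000 null and 10,000 alternative trials per R²) checks the formulas without assuming perfect balance. In each cell the formula comes first and the simulation second.

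| R² of strata | t-test type I error | t-test power | ANCOVA power |
|---|---|---|---|
| 0.05 | 0.045 / 0.044 | 0.76 / 0.76 | 0.78 / 0.78 |
| 0.12 | 0.037 / 0.038 | 0.77 / 0.77 | 0.81 / 0.80 |
| 0.30 | 0.020 / 0.021 | 0.79 / 0.79 | 0.89 / 0.88 |

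Simulated ANCOVA type I error was 0.049 to 0.050 over these three values.

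**What the choice between the tests costs.** The same simulation, per contrast:

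| R² of strata | Tests disagree at 0.05, no effect | Tests disagree, d = 0.8 | Type I error if either test may be used |
|---|---|---|---|
| 0.05 | 1.0% | 2.8% | 0.052 |
| 0.12 | 1.4% | 4.4% | 0.051 |
| 0.30 | 2.9% | 9.7% | 0.050 |

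The Monte Carlo standard error of the last column is √(0.05 × 0.95/20,000) = 0.0015, so these values are barely distinguishable from 0.05. The reason is that the two statistics have nearly the same numerator and the t-test usually has the larger denominator. Trials in which only the t-test is significant are therefore rare.

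**The case against.** Three stronger readings are tempting, and the documents do not support them.

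A reader might infer that the SAP abandons the protocol's analysis. It does not: for cortisol and STAI the stratum-adjusted ANCOVA is present and listed first. Section 7.3 names the t-test only for demographics but does not say that ANCOVA is the only test allowed. The departure is an added test without a label. A substitution occurs only for cognitive appraisal.

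A reader might infer that two p-values per contrast open the way to false positives. The check shows otherwise: the t-test errs conservatively, and taking the better of the two leaves type I error at about 0.05.

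A reader might take 12% as the share of cortisol or STAI variance explained by the strata. Protocol 7.2 takes that figure from an earlier teaching trial for its sample size, and does not attribute it to the two strata or to these outcomes. Cortisol is analysed as a within-day change, which removes stable differences between people, so the strata may explain little. At 5% the loss of power is about 0.02.

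It is also fair to say that these are secondary outcomes, that the primary analysis is untouched, and that Protocol 8.2 describes all aspects of the study as hypothesis generating. All of this limits the size of the point. What stands is that the plan does not name the governing result, and that one of its two candidates has too wide an error bar.

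**Conclusion.** The point holds as a modest one. For cortisol and STAI the plan carries a redundant group test that ignores the stratified design, with no statement of which result is to be reported. If the t-test were reported, its type I error would be about 4.4%, 3.7% or 2.0%. Power at d = 0.8 would be about 0.76, 0.77 or 0.79 instead of 0.78, 0.80 or 0.88, for R² of 5%, 12% or 30%. The harm is lost precision and ambiguity in reporting, not false positives, and it is confined to secondary outcomes.

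The size rests on the assumed R² range, on the borrowed effect size, on 46 evaluable people and, in the simulation, on strata of roughly equal size. The direction does not depend on the particular R²: the t-test is too wide whenever the strata predict the outcome.

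**What to change.** In the SAP, under Secondary Outcome 2, state that the stratum-adjusted ANCOVA already specified is the sole inferential comparison of death with survival at each time point, for cortisol change and for STAI. Delete the unpaired t-tests, or keep them under an explicit descriptive label without inferential use. For cognitive appraisal, replace the between-group t-tests by the same ANCOVA, so that all three stress measures follow Protocol 7.3.

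The cost is a few lines of SAP text. No data, visits or sample size change. The one trade is 2 degrees of freedom for the two covariates (44 to 42), which the ANCOVA power figures above already include.

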Cognitive appraisal will be measured at the end of each scenario briefing and immediately after the scenario using the method described by Tamoka et al. and evaluated for the use in simulation by Harvey et al.^{10,27,28} Primary appraisal (demand) will be measured by asking the question “How demanding do you expect the upcoming task to be?” before the scenario and “How demanding was the task you just completed?” after the scenario. Secondary appraisal (resources) will be assessed at both times by asking “How able are/were you to cope with this task?” 10 point Likert-like scale will be used for this assessment. A cognitive appraisal index will be calculated thereafter by dividing results of primary appraisal by results of secondary appraisal. An index <1 will indicate that resources do not meet demands and the task is appraised as “threat” while an index >1, where resources are greater than demands will indicate a “challenge”.

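### The appraisal index is tested as a mean ratio against 1, but when demand and resources share a distribution the mean ratio exceeds 1, so 1 is not that test's null value

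*SAP*

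**What the plan says.** Protocol section 6.1.3 (Cognitive Appraisal) asks one question on demand and one on ability to cope: "10 point Likert-like scale will be used for this assessment". The end points are not printed. The two answers become a quotient: "A cognitive appraisal index will be calculated thereafter by dividing results of primary appraisal by results of secondary appraisal". The value 1 separates the two appraisal states: "An index <1 will indicate that resources do not meet demands", which the protocol labels threat, and values above 1 are labelled challenge.

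On timing, "Cognitive appraisal will be measured at the end of each scenario briefing and immediately after the scenario". With two scenarios that gives four time points.

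The SAP (Secondary Outcome 2, Measure 3) averages the ratios by group and time point. Each mean is then "subjected to a one-sample t-test to determine whether they are significantly different from 1". A second bullet compares the two groups' mean ratios by unpaired t-test. Neither document mentions a log transform, a difference score, a geometric mean or a median for this index.

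**The concern.** A ratio of two bounded scores is not symmetric about 1. On 1-10 items, one side is squeezed into 0.1 to 1 while the other runs from 1 to 10. A participant scoring 8 and 4 gives 2.0, and the mirror-image participant scoring 4 and 8 gives 0.5. Together they balance exactly, yet their mean ratio is (2.0 + 0.5)/2 = 1.25.

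The one-sample test asks whether a group sits away from neutral. If a neutral group's expected value is already above 1, the test errs in two ways. It declares some balanced groups to be above 1, and it tends to miss groups that truly lie below 1. Telling threat from challenge is the purpose of the index, and the test is repeated in 2 groups at 4 time points, 8 times in all.

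**Working it through.** **Sample size per arm.** Protocol section 7.2 sets the design: "We aim at a two-tailed level of significance of $p < 0.05$ and a power of 0.8", an "effect size of 0.8, which is considered large and acceptable for a teaching intervention", and ANCOVA "with an estimated r^2 of 0.12". A two-sample t-test with d = 0.8 needs 26 per arm. Then 52 x (1 - 0.12) = 45.76, which rounds up to the stated 46. Adding 20% gives 46 x 1.2 = 55.2, consistent with the stated 56. With 1:1 allocation that is 23 evaluable or 28 recruited per arm. The documents give no operating figure for the appraisal test, so I assume two-sided 5% applies.

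**Why the null value is off.** Let D be demand and R resources.
- If D and R have the same distribution, E[log D] = E[log R], so E[log(D/R)] = 0.
- By Jensen's inequality, E[D/R] >= exp(0) = 1, with equality only if every participant gives D = R.
- The same holds for E[R/D], so the result does not depend on which item is on top.
- On the same premise, E[D - R] = 0 and E[log(D/R)] = 0, so 0 is the right null value on either of those scales.

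**Size, under assumed item distributions.** Scores were simulated as normal, rounded and limited to 1-10, with the same mean and SD for both items and at least 20,000 trials per setting. Some settings at n = 23 (rejection in %, nominal 5; small differences are rounding):

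| Mean | SD | Corr. | Mean ratio | Ratio vs 1: high side | Low side | Total | Log vs 0 | Difference vs 0 |
|---|---|---|---|---|---|---|---|---|
| 7 | 1 | 0.5 | 1.01 | 4.3 | 1.4 | 5.7 | 4.8 | 5.0 |
| 7 | 1.5 | 0 | 1.06 | 6.9 | 0.8 | 7.7 | 5.2 | 5.2 |
| 7 | 2 | -0.3 | 1.15 | 8.5 | 0.5 | 9.0 | 4.7 | 5.0 |
| 6 | 2 | 0 | 1.18 | 8.1 | 0.5 | 8.7 | 4.7 | 4.7 |

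At n = 28 the last three settings reject in 8.7%, 11.6% and 11.7%.

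Over the whole grid (mean 5.5-7, SD 1-2, correlation -0.3 to 0.5), the mean ratio is about 1.01-1.30. Rejection is about 5.5-11% at n = 23 and 6-15% at n = 28. The top end is one corner: mean 5.5, SD 2, correlation -0.3.

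Independent uniform scores are an extreme case outside this grid. They give E[D] x E[1/R] = 5.5 x 0.2929 = 1.61.

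**Power in the two directions** (SD 2, correlation 0, n = 23, the two means placed evenly around 6):
- Demand one point higher: the mean ratio is 1.44, detected in 54.5% of trials.
- Resources one point higher: the mean ratio is 0.975, detected in 12.1%.
- On the log or difference scale, either gap is detected in about 34-36%.
- Resources half a point higher: the mean ratio is still 1.07, on the wrong side of 1. The low side is detected in 3.2%, against 11.7% on the log scale.

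**If balance means only equal means.** With mean 6, n = 28, demand SD 2 and resources SD 1:
- At correlation 0.5 the mean ratio is 1.00 and the ratio test rejects in 5.2%.
- At correlation 0.8 the mean ratio is 0.98 and the ratio test rejects in 5.7%. The log test against 0 rejects in 10.5%.
- With the SDs reversed and correlation 0, the ratio test rejects in about 15%.

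The difference score stayed at 4.6-5.4% throughout, including the unequal-SD settings.

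**The case against.** The strongest objection is that the size is entirely assumed. No item distribution is given, and the inflation falls to about 5.5-6% with small spread or moderate positive correlation. At correlation 0.8 it is 4.9-6.0%, essentially nominal. This stands, and it is why the result is given as a range that starts near 5%. It does not remove the lean to the high side. In the mildest row of the table, 4.3 of 5.7 points (75%) still fall there.

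A second objection is that the result needs both items to have the same distribution. A reader might infer that any group with equal mean demand and mean resources is pushed above 1. That is too strong: the unequal-SD settings give 1.00 and 0.98.

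A reader might also infer that the unpaired comparison of the two groups is distorted. The documents do not support this. Under equal distributions the upward shift is common to both arms, and that test rejects in 4.0% of trials. With SD 1.5 in one arm and 2.5 in the other it rejects in 6.9%. The randomised comparison is not where the problem lies.

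Protocol section 7.3 defends parametric tests for Likert-like scales. That covers the items, not a quotient of two of them. Section 8.2 calls all aspects hypothesis generating, which lowers the stakes but does not make 1 the right null value.

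**Conclusion.** The point holds for the one-sample tests. When demand and resources share a distribution, 1 is not the expected value of the mean ratio. That part is algebra. The amount is conditional on 1-10 items and the assumed means, SDs and correlations. The false-positive rate is usually modest, about 5.5-11% at 23 per arm and up to about 15% at 28. The lopsided power (54% against 12% in the case shown) is the larger practical harm.

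The primary outcome is untouched. Cognitive appraisal is one of three stress measures within one secondary outcome (Protocol section 7.1.2).

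A reader might go on to say which appraisal state the bias favours. The documents do not allow that yet. With demand divided by resources, a shortfall of resources gives an index above 1, but section 6.1.3 labels values below 1 as the shortfall. As printed, the upward shift would be read as challenge; by the arithmetic it means that demand exceeds resources. The labels and the division must be reconciled before direction is read from any test against 1.

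**What to change.** In Measure 3 of the SAP:
1. Replace the one-sample test of the mean ratio against 1 with a one-sample test of demand minus resources against 0, and compare the arms on the same scale.
2. Alternatively, test log(demand/resources) against 0 and report geometric mean ratios, for which neutral stays at 1. If this is chosen, state that it is centred on 0 only when both items share a distribution, and that it needs a scale without 0.
3. Print the end points of the two items.
4. Reconcile the threat and challenge labels in Protocol section 6.1.3 with the direction of the division.

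The cost is a few lines of wording, mainly in the SAP. No new data are needed, since both item scores are already collected. The threat/challenge reading survives as the sign of the difference.

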unexpected death of the mannequin may occur in a simulation session in which the learner does not correctly manage the situation.^{16,17} The use of unexpected death in simulation is unsupported by evidence.^{15,16,18} Educators in favour of its use propose that unexpected death may help to cement the event as memorable² and thereby enhance learning.^{3,12} The other side of the discussion fears that unexpected death in simulation will exacerbate negative emotions and subject learners to undue stress, including the physical manifestations of stress. Such an experience could also cause psychological damage to participants or lead them to withdraw from simulation research.^{16,18,19} To date, the literature discussing the impact of simulated death on learning has been limited to retrospective surveys and opinion pieces.^{15,16,20} The true effect that unexpected death has on stress levels, performance and retention remains to be seen.

This study aims to elucidate the effect of unexpected death in a simulation scenario on the retention of crisis management skills. We hypothesize that unexpected death will be detrimental to the retention of these skills and will result in increased stress and negative emotions among participants.

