differ slightly in order to eliminate the potential for this recall bias described above. In summary, the scenarios are of equal complexity, but differ primarily with respect to the clinical context, initial cardiac arrest rhythm and pre-determined outcome (Appendix C).

Two well-trained confederates will act as registered nurse and as respiratory therapist within the team. These roles were prescribed to ensure standardization for each participant. The confederates will be instructed to help and to perform tasks when directed but not to offer crisis management advice or differential diagnoses. An individualized, video-assisted, instructor-led, structured debriefing lasting 30 minutes will follow the initial scenario. As suggested by Gaba, highly experienced and well prepared instructors will lead the debriefing phase in order to deal with potential upcoming emotions and issues.¹⁹ All scenarios and debriefings will be video recorded for performance analysis.

Retention Test

Previous data have shown that, even with high-fidelity simulation, resuscitation knowledge and skills deteriorate between as early as 2 weeks and 1 year after the learning intervention, with a faster decay in skill.^{21,22} Therefore a retention test is planned 3 months after the initial test. After a short accommodation phase of 15 minutes and assessment of baseline data a standardized scenario briefing will be done. Participants from both groups will be asked to be team-leader in a cardiac arrest scenario to test for skill retention. Again, two confederates, one acting as registered nurse and one acting as respiratory therapist will be team members. While the scenarios will be the same as in the initial test, the case presentation of the scenario and the mannequin “outcome” will be switched for the retention test. The mannequin will survive for the “unexpected death” group and it will die in the “survive” group. That way, each participant will be exposed to simulation death in the study once. To maximize learning opportunities for participants in this study, an individualized debriefing with a specially trained facilitator will follow the retention test as well.

All scenarios and debriefings will be video recorded for further performance analysis.

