6.1.4 Emotion Assessment

Emotions are inevitably linked to the occurrence of expected and unexpected death while treating a patient or patient simulator.¹⁶ As these feelings may foster or impair the learning effect, emotions that occurred throughout the simulation scenarios will be assessed. Participants will be asked to classify their emotions they experienced throughout the study by using the established Positive and Negative Affect Schedule (PANAS) at the end of each scenario. This assessment will be done immediately after debriefing of the respective scenarios.

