Five-point Likert scale

Repeated measures ANCOVA:

- Dependent variable: Score for each emotion
- Independent variable: Death vs. survival
- Covariates: Junior vs. senior; Acute vs. non-acute
- Time points: Initial and retention

For all Outcomes:

Relationships between all outcomes (determined by ANCOVA or by Pearson’s correlation) will be presented in a matrix table.

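### The two-visit repeated-measures ANCOVA for emotions has no rule for participants with only the initial visit; fitted in its classical form it would discard about 11 of 56 observed initial-test scores, a loss that is avoidable.

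*SAP*

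**What the plan says.** Under Secondary Outcome 3 (valence of emotions), the SAP specifies a "Repeated measures ANCOVA". The outcome line reads "Dependent variable: Score for each emotion", the visits are given as "Time points: Initial and retention", group is the independent variable, and the two stratification factors are covariates. It gives no other group comparison for emotions. Protocol section 7.3 names ANCOVA for the outcomes without a repeated-measures form.

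On timing, Protocol section 6.1.4 says of PANAS: "This assessment will be done immediately after debriefing of the respective scenarios". Section 6 says: "Therefore a retention test is planned 3 months after the initial test". Section 7.2 says: "In order to account for an estimated attrition rate of 20% we need to recruit 56 participants".

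Neither document defines an analysis set, a missing-data rule or a separate initial-visit analysis of emotions. Protocol section 5.1.4 allows withdrawal at any time but does not say how data already collected are used. For cortisol, STAI and cognitive appraisal, the SAP compares the groups at each time point, so a participant's initial-test values can be used without a second visit.

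**The concern.** A participant who completes the initial test has an emotion score on file about three months before attrition can take effect. The classical repeated-measures ANCOVA, with visit as a within-person factor, needs both values and removes anyone who lacks one. Participants who do not return would therefore lose a score already observed.

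The initial test matters because it is the contrast taken before the mannequin outcomes are switched between groups, and Protocol section 4.2 hypothesises more negative emotions after simulated death. Return is a post-randomisation event. The protocol's Background reports the fear that unexpected death could harm participants or "lead them to withdraw from simulation research". If return depends on how upset a person was, an analysis restricted to returners compares selected groups. If it does not, the cost is precision only.

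**Working it through.** **1. The plan's own figures.** Inputs from Protocol section 7.2: d = 0.8, two-sided alpha 0.05, power 0.8, r² = 0.12, attrition 20%. A two-sample t-test needs 52 in total, and 52 × (1 − 0.12) = 45.8, so 46. Power at 46 with r² = 0.12 is 0.81. This matches "a number of 46 participants would be needed". Then 46 × 1.2 = 55.2, so 56. Both figures reproduce. They were set for the primary outcome; no figure is given for emotions.

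**2. Scores lost under a complete-pairs fit.** 56 × 0.20 = 11.2 lost and 56 × 0.80 = 44.8 kept, so about 11 lost and 45 kept.

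**3. Precision of the initial-test contrast.** With equal arms, SE in SD units = sqrt(4/N) × sqrt(1 − r²). Using r² = 0.12 for emotions is an assumption carried over from the primary outcome.

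| N | SE | Power if d = 0.8 | Power if d = 0.5 |
|---|---|---|---|
| 56 | 0.251 | 0.88 | 0.50 |
| 45 | 0.280 | 0.80 | 0.42 |

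The SE ratio is sqrt(56/44.8) = 1.118, about 12% larger, whatever r² is. Both d values are assumptions for emotions.

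**4. Possible bias.** None of these inputs is in the documents except the 20%. Take negative affect at the initial test as normal with SD 1 in each arm and a true difference of 0.8. Let the log-odds of dropout rise by b per SD of negative affect. The returners' difference is the death-arm mean minus the control-arm mean, each weighted by the probability of returning.

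| b | Same relation in both arms, 20% overall | Affect-related in death arm only, 20% lost there |
|---|---|---|
| 0 | 0.80 | 0.80 |
| 0.5 | 0.77 | 0.70 |
| 1 | 0.71 | 0.63 |
| 2 | 0.61 | 0.54 |

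In the last column, control-arm loss is taken as unrelated to affect. The shift toward zero is nil at b = 0. Over the rest of the table it runs from 0.03 to 0.19 SD in the symmetric case and from 0.10 to 0.26 SD in the one-sided case.

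**5. Which term answers the question.** At the retention test the mannequin survives for the death group and dies for the survive group. A group main effect over both visits therefore averages two contrasts with opposite exposures. The SAP does not say which term will be tested. The initial-test question is answered by the group contrast at that visit.

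**The case against.** The strongest reply is that the SAP nowhere says non-returners are excluded. It names a method but no estimation approach, software or analysis set, and a mixed-model fit with the same terms would keep every initial score. That is correct, so the loss has to be stated as conditional. It does not clear the plan, because deletion is the usual behaviour of the named method and nothing in either document overrides it.

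Four further objections have weight:

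- **Other outcomes need both visits too.** Protocol section 7.1.1 defines the primary outcome as a change between the two tests, so emotions are not unique. There the need for two visits follows from the definition of the endpoint; for an initial-test emotion contrast it does not.
- **The objective may point to the retention visit.** Secondary objective (ii) in section 4.2 concerns future stress and emotions, and non-returners have no score at that visit. The broader hypothesis in the same section still makes the initial contrast relevant.
- **Withdrawal is reported as one side's fear in a debate.** It is not this trial's expectation, and section 7.2 gives no cause for the 20%. Section 6.4.2 points the other way: in earlier studies with over 400 participants, stress returned to baseline, and residual negative emotion came from reflection on performance.
- **PANAS follows the debriefing.** It measures emotion after that session, so calling the initial contrast the acute effect of death would be loose.

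**Conclusion.** The gap is real and cheap to close. If the repeated-measures ANCOVA is fitted classically, about 11 of 56 observed initial-test PANAS scores are lost at the planned attrition, and the standard error of the initial-test contrast is about 12% larger. Those two figures rest only on the 20% attrition and on the classical fit.

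A reader might go further and infer that the plan prescribes deletion, or that the initial contrast will be biased toward no effect. The documents support neither. The fitting method is unstated, and no link between emotion and dropout is given. The range for an assumed 0.8 SD difference runs from no bias to a returners' difference of 0.54, and the lower values require affect-related loss in the death arm only.

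The point concerns one secondary outcome in a study that describes all its aspects as hypothesis generating (Protocol section 8.2). The primary result is not touched.

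**What to change.** In the SAP, replace the repeated-measures ANCOVA under Secondary Outcome 3 with a linear mixed model fitted by likelihood to all observed PANAS scores. Fixed effects: group, visit, group × visit and the two stratification factors. Use an unstructured 2 × 2 covariance within participant.

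State that the group contrast will be reported at each visit, that the initial-visit contrast uses everyone with an initial score, and that the group main effect will not be used for inference because it averages over the switched outcomes. Report the number of initial scores without a retention score, by arm. For the retention-visit contrast, state the assumption that dropout depends only on observed data, including the initial score.

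The cost is a few lines of SAP text: no new data, no change in sample size, standard software.
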